6.4.2 Recommended Dose Modifications for Lenalidomide Treatment Associated Toxicity

For a new cycle of treatment to begin, the patient must meet the following criteria:

- ANC must be $\geq 1,000/\text{mm}^3$.
- Platelet count must be $\geq 75,000/\text{mm}^3$.
- All other nonhematologic toxicity (except for alopecia) or peripheral neuropathy must have resolved to \leq Grade 1 or to the patient's baseline condition.

The maximum delay before treatment should be discontinued will be 30 days post original planned start of the cycle or at the discretion of the Principal Investigator.

Dose reduction schemas for Lenalidomide

**Fred Hutchinson Cancer Research Center
Clinical Study Protocol [FHCRC 9266]**

**Fred Hutchinson Cancer Research Center
Clinical Study Protocol [FHCRC 9266]**

Table 6.4: Dose reduction schema for Lenalidomide cycles

Due to Adverse Events (Hematologic Toxicities)		
ANC \leq 500 and/or platelets \leq 30,000 cells/mm ³ (Other than Day 1)	Hold to ANC \geq 1000 and platelets \geq 75,000 cells/mm ³ , then dose reduce	1 st dose reduction(DR): 21 days instead of 28 days 2 nd DR: 5 mg po 21 days on, 7 days off 3 rd DR 5 mg po qod

Fred Hutchinson Cancer Research Center
Clinical Study Protocol [FHCRC 9266]

Table 6.5: Dose reduction schema for Lenalidomide cycles, by Grade

Due to Adverse Events (Non-Hematologic Toxicities)			
Adverse Event (Severity)	Action on Study Drug	Further Considerations	Dose De-Escalation Schedule
Peripheral Neuropathy:			
Grade 1 peripheral neuropathy	No action	Grade 1 signs and symptoms: asymptomatic; without pain or loss of function; clinical or diagnostic observations only [7]	1 st dose reduction(DR): 21 days instead of 28 days
New or worsening Grade 1 peripheral neuropathy with pain or Grade 2	Hold study drug until resolution to Grade ≤ 1 without pain or baseline	Grade 2 signs and symptoms: Moderate symptoms; limiting instrumental activities of daily living (ADL) [7]	2nd DR: 5 mg po 21 days on, 7 days off
New or worsening Grade 2 peripheral neuropathy with pain or Grade 3	Hold study drug until resolution to Grade ≤ 1 without pain or baseline Reduce study drug to next lower dose upon recovery	Grade 3 signs and symptoms: severe symptoms; limiting self-care ADL; assistive device indicated [7]	3rd DR 5 mg po qod
New or worsening Grade 4 peripheral neuropathy	Discontinue study drug		
Rash Grade 2	Symptomatic recommendations as per Section 6.10	At the discretion of the investigator, may require dose modification.	
Grade 3 nonhematologic, nonperipheral neuropathy toxicity judged to be related to lenalidomide	Hold study drug until resolution to Grade < 1 or baseline	Symptomatic recommendations noted in Section 6.7	
If not recovered to $<$ Grade 1 or baseline within 30 days	Reduce study drug 1 to next lower dose upon return to $<$ Grade 1 or baseline		
Subsequent recurrence Grade 3 that does not recover to $<$ Grade 1 or baseline within 30 days	Hold study drug until resolution to Grade < 1 or baseline Reduce study drug to next lower dose	Monitor closely, take appropriate medical precautions, and provide appropriate symptomatic care	
Grade 4 nonhematologic, nonperipheral neuropathy toxicities judged to be related to lenalidomide	Consider permanently discontinuing lenalidomide	Exceptions are cases in which the investigator determines the patient is obtaining a clinical benefit	

**Fred Hutchinson Cancer Research Center
Clinical Study Protocol [FHCRC 9266]**

Once lenalidomide is reduced for any toxicity, the dose may not be re-escalated.

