Symptomatic measures such as antihistamines or corticosteroids (oral or topical) have been successfully used to manage rash and have been used prophylactically in subsequent cycles. The use of a topical, IV, or oral steroid (e.g., prednisone \leq 10 mg per day or equivalent) is permitted. Management of a Grade 3 rash may require intravenous antihistamines or corticosteroids. Administration of ixazomib or lenolidamide should be modified per protocol and re-initiated at a reduced level from where rash was noted (also, per protocol).

In line with clinical practice, dermatology consult and biopsy of Grade 3 or higher rash or any SAE involving rash is recommended. Prophylactic measures should also be considered if a patient has previously developed a rash (e.g., using a thick, alcohol-free emollient cream on dry areas of the body or oral or topical antihistamines). A rare risk is Stevens-Johnson Syndrome, a severe and potentially life-threatening rash with skin peeling and mouth sores, which should be managed symptomatically according to standard medical practice. Punch biopsies for histopathological analysis are encouraged at the discretion of the investigator.

Thrombocytopenia

Blood counts should be monitored regularly as outlined in the protocol with additional testing obtained according to standard clinical practice. Thrombocytopenia may be severe but has been manageable with platelet transfusions according to standard clinical practice. Ixazomib and lenalidomide administration should be modified as noted as per dose modification recommendations in the protocol when thrombocytopenia occurs (see Table 6-2). Therapy can be reinitiated at a reduced level upon recovery of platelet counts. A rare risk is thrombotic thrombocytopenic purpura (TTP), a rare blood disorder where blood clots form in small blood vessels throughout the body characterized by thrombocytopenia, petechiae, fever, or possibly more serious signs and symptoms. TTP should be managed symptomatically according to standard medical practice.

Neutropenia

Fred Hutchinson Cancer Research Center
Clinical Study Protocol [FHCRC 9266]

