6.12 Packaging and Labeling

The study drug ixazomib capsules will be provided by Millennium. The study drug will be labeled and handled as open-label material, and packaging labels will fulfill all requirements specified by governing regulations.

The capsules are individually packaged using cold-form foil-foil blisters that are in a child-resistant carton. There are 3 capsules in each wallet/carton.

Lenalidomide will be supplied as commercial product. Standard recommendations from package insert will be followed (See appendix 12.3).

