4.2 Allergic Reactions

REVLIMID is contraindicated in patients who have demonstrated hypersensitivity (e.g., angioedema, Stevens-Johnson syndrome, toxic epidermal necrolysis) to lenalidomide [*see Warnings and Precautions (3.8)*].

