5.8 Allergic Reactions

Angioedema and serious dermatologic reactions including Stevens-Johnson syndrome (SJS) and toxic epidermal necrolysis (TEN) have been reported. These events can be fatal. Patients with a prior history of Grade 4 rash associated with thalidomide treatment should not receive REVLIMID. REVLIMID interruption or discontinuation should be considered for Grade 2-3 skin rash. REVLIMID must be discontinued for angioedema, Grade 4 rash, exfoliative or bullous rash, or if SJS or TEN is suspected and should not be resumed following discontinuation for these reactions.

REVLIMID capsules contain lactose. Risk-benefit of REVLIMID treatment should be evaluated in patients with lactose intolerance.

Fred Hutchinson Cancer Research Center

Clinical Study Protocol [FHCRC 9266]

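### Table 6.5 has no mandatory stop for the severe skin and allergic reactions after which the appended insert bars resuming lenalidomide

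*Combined protocol and SAP*

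**What the plan says.** Table 6.5 in Section 6.4.2 sorts lenalidomide toxicity by grade. For related toxicity that is neither hematologic nor peripheral neuropathy, the Grade 4 action is "Consider permanently discontinuing lenalidomide", and the column beside it adds: "Exceptions are cases in which the investigator determines the patient is obtaining a clinical benefit". The Grade 3 action is to hold the drug until the event clears, with a dose reduction if clearing takes longer than 30 days. Grade 2 rash gets symptomatic care, with dose changes at the investigator's discretion. No row names angioedema, exfoliative or bullous rash, SJS or TEN.

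Section 6.10, under its rash heading, states: "Administration of ixazomib or lenolidamide should be modified per protocol and re-initiated at a reduced level from where rash was noted". The next paragraph mentions SJS as a rare, potentially life-threatening rash with "skin peeling and mouth sores, which should be managed symptomatically according to standard medical practice".

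The lenalidomide insert, reproduced in Appendix 12.3, is stricter for a short list of reactions. Insert 5.8: "REVLIMID must be discontinued for angioedema, Grade 4 rash, exfoliative or bullous rash, or if SJS or TEN is suspected and should not be resumed". Insert 4.2: "REVLIMID is contraindicated in patients who have demonstrated hypersensitivity (e.g., angioedema, Stevens-Johnson syndrome, toxic epidermal necrolysis) to lenalidomide". Section 6.12 (Packaging and Labeling) says of lenalidomide: "Standard recommendations from package insert will be followed (See appendix 12.3". Section 1.11 also refers the reader to the insert for risks.

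**The concern.** A clinician handling a skin or allergic reaction will turn to the dose-modification table. For Grade 4 rash, that table leaves the stop to judgment and lets a perceived benefit override it, whereas the insert makes the stop mandatory. For the other listed reactions the table is silent, so the generic rows apply, and the Grade 3 row leads to resumption. The insert says these reactions can be fatal. What is at stake is re-exposure of a patient to a drug that the protocol's own appendix says must not be given again.

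There is a smaller consequence for the primary safety count. Lenalidomide is first given in cycles 3-4, inside the four-month window of Section 7.1.7. The protocol does not say what happens to a patient who must stop lenalidomide for good but could still take ixazomib.

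**Working it through.** The plan gives no figure for these reactions, so the main check sets the two sets of instructions side by side.

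| Reaction | Table 6.5 as written | Insert |
|---|---|---|
| Grade 4 rash | Grade 4 row: stopping to be considered, benefit exception | Stop, no resumption (5.8) |
| Exfoliative or bullous rash, Grade 3 | Grade 3 row: hold, then resume | Stop, no resumption (5.8) |
| Exfoliative or bullous rash, Grade 2 | Grade 2 rash row: symptomatic care, discretion on dose | Stop, no resumption (5.8) |
| Angioedema | Grade 3 or 4 row by severity; no row below Grade 3 | Stop, no resumption (5.8); contraindicated (4.2) |
| Suspected SJS or TEN | Grade 3 or 4 row by severity | Stop, no resumption (5.8); contraindicated once demonstrated (4.2) |

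The first row is a plain contradiction. The others arise because the table has no exception to its generic rules.

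The conflict goes no further than this list. For other Grade 3/4 toxicity in myeloma, insert 2.1 itself allows a restart at a lower dose at the physician's discretion. For Grade 2-3 rash without these features, insert 5.8 asks only that interruption or discontinuation be considered. Grade 4 peripheral neuropathy already carries a mandatory stop in Table 6.5, so a mandatory row fits the table's format.

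**How often the rash rows might be reached.** The insert reports Grade 3/4 rash of any kind in several lenalidomide populations. With n = 30, the expected number is 30 × p and the chance of at least one case is 1 − (1 − p)^30.

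| Source in insert | p | 30 × p | 1 − (1 − p)^30 |
|---|---|---|---|
| Mantle cell lymphoma, single agent (Table 10) | 2/134 = 1.5% | 0.45 | .36 |
| Del 5q MDS, 10 mg start (Table 9) | 10/148 = 6.8% | 2.0 | .88 |
| Newly diagnosed myeloma, 25 mg plus dexamethasone, continuous arm (Table 4) | 39/532 = 7.3% | 2.2 | .90 |

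Applying these rates to post-transplant maintenance is an assumption; populations, doses and co-medication differ. They also cover every Grade 3/4 rash. The part that is Grade 4, exfoliative, bullous or SJS/TEN is not given, nor is a rate for angioedema.

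**Section 7.1.7.** Because the fix touches the withdrawal count, I checked the stated stopping probabilities. An exact sequential binomial calculation over the six listed boundaries (2/5, 3/10, 4/15, 5/20, 6/25, 7/30) gives, by 15 and by 30 patients, .030/.031 at a true rate of 5%, .129/.146 at 10% and .775/.912 at 30%. These match the plan's .03/.03, .13/.15 and .78/.91.

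**The case against.** The strongest reply is that this is ordinary drafting. The insert has the same structure: a generic hold-and-restart line for Grade 3/4 toxicity in its dosing section, overridden by a specific warning elsewhere. Table 6.5 is headed as recommended modifications, the insert is appended in full, and 6.12 and 1.11 point to it. Section 6.15 lets the investigator withdraw a patient for qualifying grade IV toxicity or for treatment that looks detrimental, and exclusion criterion 11 screens out known allergy.

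Much of this stands as mitigation. It does not settle the matter. Section 6.12 is one general sentence under packaging and does not say that it prevails over the table. Section 6.15 gives a right, not a duty, and its toxicity item covers only grade IV. Criterion 11 acts only at entry. None of these removes the benefit exception for Grade 4 rash. The insert's Highlights tie the ban on resumption to verified reactions, slightly looser than 5.8, but still do not allow restart after a verified one.

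Three stronger readings are tempting and should be resisted.

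- A reader might infer that 6.10 authorises restart after SJS. It does not. The re-initiation sentence concerns ordinary rash, which that section describes as usually Grade 1 to 2, and the SJS sentence concerns care of the reaction. The defect is narrower: the rash sentence has no exception, and the SJS text has no stop rule.
- A reader might infer that the Grade 3 row's pointer, "Symptomatic recommendations noted in Section 6.7", is an error. That is not shown. The row covers all non-hematologic toxicity, and 6.7 lists antiemetics, antidiarrheals and supportive measures. The Grade 2 rash row already points to 6.10.
- A reader might infer that keeping grade IV patients on drug weakens the stopping rule by a calculable amount. The documents give no share of patients retained, so any such figure would rest on invented inputs. Counting withdrawals is the stated design, and its probabilities reproduce.

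**Conclusion.** The point holds in a limited form. For Grade 4 rash, Table 6.5's discretion and benefit exception contradict the appended insert. For angioedema, exfoliative or bullous rash and suspected SJS/TEN, the table is silent and its generic rows allow a restart that the insert rules out. Other parts of the protocol make re-exposure less likely without closing the gap.

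Frequency cannot be stated for the reactions that matter. The .36 to .90 range describes any Grade 3/4 rash under borrowed rates and is only an outer frame. The case for changing the text rests on the severity of the reactions and the small cost of the fix. It is not a finding against the operating characteristics in 7.1.7.

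**What to change.** 1. Add a row to Table 6.5: permanently discontinue lenalidomide, at any grade and with no benefit exception, for angioedema, Grade 4 rash, exfoliative or bullous rash, and suspected SJS or TEN, citing insert 4.2 and 5.8.
2. Make the rash and SJS text in 6.10 refer to that row.
3. State whether a patient permanently off lenalidomide may continue ixazomib or is withdrawn from study therapy and, if this falls in the first four months, whether the case counts as a toxicity withdrawal under 7.1.7. The Protocol Summary also counts patients who cannot resume therapy by 30 days, so the text should say whether taking ixazomib alone counts as resuming.
4. Optional: point the Grade 3 row to 6.10 as well as 6.7.

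The cost is one table row, a cross-reference and a sentence or two. No new data are needed and the stopping boundaries stay as they are, although the answer to item 3 may change which patients enter the count. The downside is some loss of investigator discretion, confined to reactions for which the appendix already withholds it.

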6.5 Additional medications

Supportive care

- IV Bisphosphonates therapy as clinically indicated per Standard Practice guidelines. VZV and PCP prophylaxis to continue for 2 additional months post stopping therapy.

6.6 Excluded Concomitant Medications and Procedures

The following medications and procedures are prohibited during the study.

Systemic treatment with any of the following metabolizing enzyme inhibitors is not permitted in this study. (A drug-drug interaction [DDI] with a strong inhibitor would increase the ixazomib exposure and could lead to a higher probability of an AE):

- Strong inhibitors of CYP1A2: fluvoxamine, enoxacin, ciprofloxacin
- Strong inhibitors of CYP3A: clarithromycin, telithromycin, itraconazole, voriconazole, ketoconazole, nefazodone, and posaconazole

Systemic treatment with any of the following metabolizing enzyme inducers should be avoided, unless there is no appropriate alternative medication for the patient's use (Rationale: Unlike with inhibitors, if there were to be a DDI with an inducer, ixazomib exposure would be less; therefore, there would be a reduced chance of an AE. However, there may be less chance for an antitumor effect, but that is not an absolute reason to be taken off ixazomib):

- Strong CYP3A inducers: rifampin, rifapentine, rifabutin, carbamazepine, phenytoin, and phenobarbital
- Excluded foods and dietary supplements include St. John's wort and Ginkgo biloba

The following procedures are prohibited during the study.

- Any antineoplastic treatment with activity against Multiple Myeloma, other than study drugs
- Radiation therapy (note that, in general, the requirement for local radiation therapy indicates disease progression)
- Platelet transfusions to help patients meet eligibility criteria or prior to any dosing day are not allowed within 3 days prior to treatment administration (refer to eligibility criteria and criteria required prior to initiating next cycle of treatment or within cycle dose modifications).

6.7 Permitted Concomitant Medications and Procedures

The following medications and procedures are permitted during the study:

- Antiemetics, including 5-HT3 serotonin receptor antagonists, may be used at the discretion of the investigator.
- Loperamide or other antidiarrheal should be used for symptomatic diarrhea at discretion of the investigator. The dose and regimen will be according to institutional guidelines. IVF should be given to prevent volume depletion.
- Growth factors (e.g., granulocyte colony stimulating factor [G-CSF], granulocyte macrophage-colony stimulating factor [GM-CSF], recombinant erythropoietin) are permitted. Their use should follow published guidelines and/or institutional practice.
- Patients should be transfused with red cells and platelets as clinically indicated and according to institutional guidelines.
- Patients who experience worsening neuropathy from baseline may be observed for recovery and have dose reductions/delays as indicated in the protocol, and any supportive therapy or intervention may be initiated as appropriate at the discretion of the investigator.
- Supportive measures consistent with optimal patient care may be given throughout the study.

6.8 Precautions and Restrictions

- Fluid deficit should be corrected before initiation of treatment and during treatment.
- Nonsteroidal anti-inflammatory drugs (NSAIDs) should be avoided with impaired renal function given reported NSAID-induced renal failure in patients with decreased renal function.

Pregnancy

It is not known what effects ixazomib has on human pregnancy or development of the embryo or fetus. Therefore, female patients participating in this study should avoid becoming pregnant, and male patients should avoid impregnating a female partner. Nonsterilized female patients of reproductive age group and male patients should use effective methods of contraception through defined periods during and after study treatment as specified below.

Female patients must meet 1 of the following:

- Postmenopausal for at least 1 year before the screening visit, or
- Surgically sterile, or

**Fred Hutchinson Cancer Research Center
Clinical Study Protocol [FHCRC 9266]**

- If they are of childbearing potential, agree to practice 2 effective methods of contraception from the time of signing of the informed consent form through 90 days after the last dose of study drug, or
- Agree to practice true abstinence, when this is in line with the preferred and usual lifestyle of the subject. (Periodic abstinence [e.g., calendar, ovulation, symptothermal, post ovulation methods] and withdrawal are not acceptable methods of contraception.)

Male patients, even if surgically sterilized (i.e., status post vasectomy) must agree to 1 of the following:

- Practice effective barrier contraception during the entire study treatment period and through 90 days after the last dose of study drug, or
- Agree to practice true abstinence, when this is in line with the preferred and usual lifestyle of the subject. (Periodic abstinence [e.g., calendar, ovulation, symptothermal, post ovulation methods for the female partner] and withdrawal are not acceptable methods of contraception.)

6.9 Patients will also enroll in Revlimid REMS TM program for Lenalidomide use and followed appropriately as Revlimid is associated with birth defects.

Patients should not breastfeed on this study.

6.10 Management of Ixazomib Clinical Events

Adverse drug reactions such as thrombocytopenia, diarrhea, fatigue, nausea, vomiting, and rash have been associated with ixazomib treatment. Management guidelines regarding these events are outlined below. Further details of management of ixazomib AEs are described in Section 6 of the ixazomib IB.

Prophylaxis Against Risk of Reactivation of Herpes Infection

Patients may be at an increased risk of infection including reactivation of herpes zoster and herpes simplex viruses. Antiviral therapy such as acyclovir, valacyclovir, or other antivirals are to be given as clinically indicated in Section 6.5., i.e. acyclovir 800 mg po BID or valacyclovir 500 mg po BID.

Nausea and/or Vomiting

Standard anti-emetics including 5-hydroxytryptamine 3 serotonin receptor antagonists are recommended for emesis if it occurs once treatment is initiated; prophylactic anti-emetics may also be considered at the physician's discretion. Dexamethasone should not be administered as an anti-emetic. Fluid deficit should be corrected before initiation of study drug and during treatment.

Diarrhea

Prophylactic antidiarrheals will not be used in this protocol. However, diarrhea should be managed according to clinical practice, including the administration of antidiarrheals once infectious causes are excluded. Fluid intake should be maintained to avoid dehydration. Fluid deficit should be corrected before initiation of treatment and during treatment.

Erythematous Rash With or Without Pruritus

As with bortezomib, rash with or without pruritus has been reported with lenalidomide and also with ixazomib, primarily at the higher doses tested and when given with agents where rash is an overlapping toxicity. The rash may range from limited erythematous areas, macular and/or small papular bumps that may or may not be pruritic over a few areas of the body, to a more generalized eruption that is predominately on the trunk or extremities. Rash has been most commonly characterized as maculopapular or macular. To date, when it does occur, rash is most commonly reported within the first 3 cycles of therapy. The rash is often transient, self-limiting, and is typically Grade 1 to 2 in severity.

Symptomatic measures such as antihistamines or corticosteroids (oral or topical) have been successfully used to manage rash and have been used prophylactically in subsequent cycles. The use of a topical, IV, or oral steroid (e.g., prednisone \leq 10 mg per day or equivalent) is permitted. Management of a Grade 3 rash may require intravenous antihistamines or corticosteroids. Administration of ixazomib or lenolidamide should be modified per protocol and re-initiated at a reduced level from where rash was noted (also, per protocol).

In line with clinical practice, dermatology consult and biopsy of Grade 3 or higher rash or any SAE involving rash is recommended. Prophylactic measures should also be considered if a patient has previously developed a rash (e.g., using a thick, alcohol-free emollient cream on dry areas of the body or oral or topical antihistamines). A rare risk is Stevens-Johnson Syndrome, a severe and potentially life-threatening rash with skin peeling and mouth sores, which should be managed symptomatically according to standard medical practice. Punch biopsies for histopathological analysis are encouraged at the discretion of the investigator.

Thrombocytopenia

Blood counts should be monitored regularly as outlined in the protocol with additional testing obtained according to standard clinical practice. Thrombocytopenia may be severe but has been manageable with platelet transfusions according to standard clinical practice. Ixazomib and lenalidomide administration should be modified as noted as per dose modification recommendations in the protocol when thrombocytopenia occurs (see Table 6-2). Therapy can be reinitiated at a reduced level upon recovery of platelet counts. A rare risk is thrombotic thrombocytopenic purpura (TTP), a rare blood disorder where blood clots form in small blood vessels throughout the body characterized by thrombocytopenia, petechiae, fever, or possibly more serious signs and symptoms. TTP should be managed symptomatically according to standard medical practice.

Neutropenia

Fred Hutchinson Cancer Research Center
Clinical Study Protocol [FHCRC 9266]

Blood counts should be monitored regularly as outlined in the protocol with additional testing obtained according to standard clinical practice. Neutropenia may be severe but has been manageable. Growth factor support is not required but may be considered according to standard clinical practice. Ixazomib and lenolidomide administration should be modified as noted as per dose modification recommendations in the protocol when neutropenia occurs (see Table 6-2). Therapy can be reinitiated at a reduced level upon recovery of ANCs.

Fluid Deficit

Dehydration should be avoided since ixazomib may cause vomiting, diarrhea, and dehydration. Acute renal failure has been reported in patients treated with ixazomib, commonly in the setting of the previously noted gastrointestinal toxicities and dehydration.

Fluid deficit should be corrected before initiation of study drug and as needed during treatment to avoid dehydration.

Hypotension

Symptomatic hypotension and orthostatic hypotension with or without syncope have been reported with ixazomib. Blood pressure should be closely monitored while the patient is on study treatment and fluid deficit should be corrected as needed, especially in the setting of concomitant symptoms such as nausea, vomiting, diarrhea, or anorexia. Patients taking medications and/or diuretics to manage their blood pressure (for either hypo- or hypertension) should be managed according to standard clinical practice, including considerations for dose adjustments of their concomitant medications during the course of the trial. Fluid deficit should be corrected before initiation of study drug and as needed during treatment to avoid dehydration.

Posterior Reversible Encephalopathy Syndrome

One case of posterior reversible encephalopathy syndrome, which ultimately resolved, has been reported with ixazomib. This condition is characterized by headache, seizures and visual loss, as well as abrupt increase in blood pressure. Diagnosis may be confirmed by magnetic resonance imaging (MRI). If the syndrome is diagnosed or suspected, symptom-directed treatment should be maintained until the condition is reversed by control of hypertension or other instigating factors.

Transverse Myelitis

Transverse myelitis has also been reported with ixazomib. It is not known if ixazomib causes transverse myelitis; however, because it happened to a patient receiving ixazomib, the possibility that ixazomib may have contributed to transverse myelitis cannot be excluded.

Elevated Creatinine

Metabolism appears to be a major route of elimination for ixazomib. Urinary excretion of the parent compound is negligible. Modest transient increases in creatinine and infrequent (< 8%) cases of reversible renal failure have been reported. Two patients have required temporary dialysis for acute renal failure. One patient was treated above the MTD in Study C16001, where IV ixazomib was administered to patients with advanced solid tumors. The second patient required temporary dialysis due to ESRD related to progression of myeloma. Confounding factors include GI toxicities such as nausea, vomiting, and diarrhea, and concomitant dehydration and disease progression. As a

**Fred Hutchinson Cancer Research Center
Clinical Study Protocol [FHCRC 9266]**

result of these events, all ongoing ixazomib clinical studies were amended to increase creatinine monitoring to include clinical chemistry during the week off therapy and patient management suggestions were enhanced. Dehydration should be avoided. Appropriate supportive care that includes IV fluids to prevent fluid deficits according to standard medical practice is recommended. Non-steroidal anti-inflammatory drugs (NSAIDs) are not recommended given they may, in and of themselves, have an association to renal dysfunction.

Cough, Dyspnea, and Headache

Cases of cough, dyspnea, and headache have been reported in the clinical studies; however, the relationship of onset to ixazomib is not yet completely established in humans. Standard medical care and additional monitoring should be performed as clinically indicated.

Peripheral Edema

Cases of peripheral edema have been reported in the clinical studies, primarily in the oral combination studies. Standard medical care and additional monitoring should be performed as clinically indicated.

